2.0 Rationale and Specific Aims

The specific aim of the study is to compare the difference between the ESP block and surgeon infiltration in achieving the following:

- 1. Improved postoperative pain scores
- 2. Decreased opioid requirements
- 3. Improved patient satisfaction scores
- 4. Decreased opioid side effects (Nausea, sedation, ileus, urinary retention, respiratory depression)

The primary endpoint of this study will be VAS pain score. The VAS scores will be taken with both rest and movement.

The secondary endpoint includes intravenous opioid consumption and opioid side effects (nausea, sedation, ileus, urinary retention, respiratory depression). The IV and PO opioid doses will be quantified at 1, 24, 48, and 72 hours. We will also measure postoperative nausea and sedation scores at 1, 24, 48, and 72 hours. We will measure time to first flatus, incidence of urinary retention, incidence of respiratory depression, and time to discharge.

All patients will receive a phone survey 6 months after surgery to assess for pain and quality of life.

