5.0 Study Procedures

All the erector spinae plane blocks will be placed preoperatively after sedation, before intubation and prior to surgery. All procedures will be done using sterile technique with masks, hats, and sterile gloves. All procedures will be placed under the supervision of the attending anesthesiologist on the acute pain service or the attending anesthesiologist in the VATS room.

To perform the ESP block, an ultrasound probe is used to visualize the ES musculature about 3 cm laterally from the T5 spinous process. In a cephalad-to-caudad direction advance the needle and inject the anesthetic in the interfacial plane deep to the ES muscles. Confirm positioning by visualization of needle tip and elevation of ES muscles off the transverse process with anesthetic injection. Surgeon infiltration is performed intraoperatively under direct thoracoscopic guidance. The intercostal space will be visualized and injected with LB. Typically, T4 through T8 are infiltrated with 2-3mL of the anesthetic mixture.

All patients will receive 1gm of acetaminophen and 600mg of gabapentin preoperatively. Patients above 70yo will receive 300mg of gabapentin. General anesthesia will be induced in the operating room and the patient will be placed in the lateral position for the VATS procedure. All patients will

receive intraoperative lidocaine and ketamine which is used to decrease opioid use after surgery and is being used as part of ERAS protocol. The patients will be intubated with dual lumen endotracheal tubes and placed on one-lung ventilation for the procedure. All patients will receive intravenous patient-controlled analgesia (PCA hydromorphone) post-operatively for breakthrough pain. They will also be scheduled on PO acetaminophen. PO oxycodone PRN will be started on POD 1 once patients tolerate diet.

Opioid usage at 1,24,48,72 hours after the block will be recorded by a member of the research team. Pain scores at rest and on movement (knee flexion) will be measured by the investigator using Visual Analog Scale (VAS). Nausea will be measured using a categorical scoring system (none=0; mild=1; moderate=2; severe=3). Sedation scores will also be assessed by a member of the study team using a sedation scale (awake and alert=0; quietly awake=1; asleep but easily roused=2; deep sleep=3). All these parameters will be measured at 1, 24, 48 and 72 hours after the epidural or PVB. Patients will be encouraged to ambulate on postoperative day 1 under supervision.

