All patients will receive a phone call 6 months after surgery for assessment for chronic postsurgical pain. Patients will be assessed by a member of the research team over the phone. They will be assessed on their pain score and narcotic usage by using the Brief Pain Inventory. Study participation will conclude after the 6 month follow questionnaire has been completed.

6.0 Reporting of Adverse Events or Unanticipated Problems involving Risk to Participants or Others

Patients will be monitored by the primary team during the postoperative period which is after surgery, through hours, 24, 48, and 72. We will also follow up in 6 months with a telephone call to complete a questionnaire which will conclude all study participation. Any adverse events or unanticipated problems that are reported to the acute pain anesthesia resident who is not listed on the study will contact the Principal investigator or one of the study personnel and all events will be addressed immediately. All adverse events or unanticipated problems that meet the criteria for prompt reporting will be reported to the IRB within 5 business days.

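### The 1 to 72 h outcomes, including the primary VAS, are timed from a procedure that no arm receives, and no usable time zero common to all three arms is given

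*Combined protocol and SAP*

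**What the plan says.** Section 4.0 lists three groups: ESP block with LB, ESP block with SB, and surgeon infiltration. None is an epidural or a PVB.

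Section 5.0 sets the stage of each procedure. For ESP: "All the erector spinae plane blocks will be placed preoperatively after sedation, before intubation and prior to surgery". For the third arm: "Surgeon infiltration is performed intraoperatively under direct thoracoscopic guidance".

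The same section gives two anchors for the outcomes:

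- Opioid use: "Opioid usage at 1,24,48,72 hours after the block will be recorded by a member of the research team".
- After describing VAS, nausea and sedation: "All these parameters will be measured at 1, 24, 48 and 72 hours after the epidural or PVB". Opioid use appears earlier in that paragraph, so it can be read as one of these parameters too.

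Other sections touch on timing without fixing a start event:

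- Section 2.0: "We will also measure postoperative nausea and sedation scores at 1, 24, 48, and 72 hours". Its opioid times name no start event.
- Section 6.0, on safety monitoring: "Patients will be monitored by the primary team during the postoperative period which is after surgery, through hours, 24, 48, and 72".
- Section 8.0 gives 24 and 48 h for the primary VAS and for satisfaction, and 1 to 72 h for the other repeated measures, again with no start event.

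The 6-month call is tied to surgery and is not in question.

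**The concern.** The only anchor that the plan attaches to its primary outcome is an event that no patient in the trial undergoes. The wording looks carried over from another study. Deleting it does not settle the matter. The obvious substitute, the block, falls before surgery in two arms and during surgery in the third. If infiltration is not counted as a block, the third arm has no clock at all. Section 1.0 uses the word block for infiltration; Sections 4.0 and 5.0 do not.

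At stake is the main comparison, ESP versus infiltration. On an injection clock, the two techniques are compared at different times since surgery. Cumulative opioid totals would also cover different numbers of postoperative hours. Different staff could reasonably follow different clocks, because the text does not say which one applies.

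**Working it through.** **Step 1: the candidate clocks side by side**

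| Reading of the plan | ESP arms | Infiltration arm |
|---|---|---|
| Epidural or PVB (5.0) | event does not occur | event does not occur |
| Block (5.0), infiltration counted as a block | starts before surgery | starts during surgery |
| Block (5.0), infiltration not counted | starts before surgery | no start event |
| Postoperative clock (implied by 2.0 and 6.0) | starts after surgery | starts after surgery |

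Only the last row gives all arms the same reference point. No section states it as the rule for the outcomes.

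**Step 2: what an injection clock does**

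Let L be the time from injection to end of surgery. A reading at nominal hour t falls t − L hours after surgery. The between-arm gap is (t − L_inf) − (t − L_ESP) = L_ESP − L_inf, the same at every t. ESP is given before surgery and infiltration during it, so with comparable operation times the gap is positive on average. That direction follows from Section 5.0. The size does not, because the documents give no durations.

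**Step 3: illustration (every lag is an assumption)**

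The table shows hours after end of surgery, ESP / infiltration.

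| L_ESP, L_inf (h) | Gap (h) | Nominal 1 h | Nominal 24 h | Nominal 48 h |
|---|---|---|---|---|
| 2, 1.5 | 0.5 | −1 / −0.5 | 22 / 22.5 | 46 / 46.5 |
| 2.5, 0.5 | 2 | −1.5 / 0.5 | 21.5 / 23.5 | 45.5 / 47.5 |
| 4, 0.25 | 3.75 | −3 / 0.75 | 20 / 23.75 | 44 / 47.75 |

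A negative entry falls before the end of surgery. A VAS at rest or on knee flexion cannot be scored in a patient still under anaesthesia, so on this clock the 1 h reading fails for any ESP patient whose surgery is still running. It fails for an infiltration patient too if the injection comes more than 1 h before the end.

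**Step 4: opioid windows**

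On an injection clock, a window of W hours contains W − L postoperative hours. The ESP shortfall relative to infiltration is (L_ESP − L_inf) / (W − L_inf).

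| L_ESP, L_inf (h) | W = 24 | W = 48 | W = 72 |
|---|---|---|---|
| 2, 1.5 | 0.5/22.5 = 2.2% | 0.5/46.5 = 1.1% | 0.5/70.5 = 0.7% |
| 2.5, 0.5 | 2/23.5 = 8.5% | 2/47.5 = 4.2% | 2/71.5 = 2.8% |
| 4, 0.25 | 3.75/23.75 = 15.8% | 3.75/47.75 = 7.9% | 3.75/71.75 = 5.2% |

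These are shares of hours, not of dose. Section 5.0 says of the PCA: "All patients will receive intravenous patient-controlled analgesia (PCA hydromorphone) post-operatively for breakthrough pain". If only postoperative opioid is counted, the shorter ESP window favours ESP. If intraoperative opioid is counted, the ESP window swaps postoperative hours at its end for hours before and during surgery, and the net direction could be offset or reversed. The documents do not say which rule applies.

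**Step 5: LB versus SB**

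Both ESP arms are injected at the same preoperative stage, so whichever clock is used, it starts at the same point in both.

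**The case against.** The strongest reply is that this is one leftover phrase. Read the epidural or PVB as a stale name for the block in the same paragraph, and Section 5.0 has one badly worded injection anchor, not two competing ones. This is a fair reading, but it does not rescue the plan: an injection anchor is exactly the one that starts at a different surgical stage in each technique.

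A second reply is that a strict injection clock is unworkable at 1 h, so staff would probably count from the end of surgery. That is plausible, and then no gap in time since surgery arises. But the 24 and 48 h readings are workable on either clock, and nothing in the text secures the postoperative one.

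Three stronger readings are tempting, and the documents do not support them.

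- A reader might infer that Sections 2.0 and 6.0 set a postoperative clock that flatly contradicts Section 5.0. They only imply one. In Section 2.0 the word postoperative describes the scores, and a score 24 h after a preoperative block is normally postoperative as well. Section 6.0 concerns safety monitoring.
- A reader might infer that the plan names no time zero whatever. The block is a nominal anchor for opioid use; what is missing is one that is usable and common to all three arms.
- A reader might infer that every ESP patient would be assessed earlier than every infiltration patient. The ordering holds on average. Section 3.0 admits wedge resection, lobectomy and other VATS, so individual lags will vary.

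**Conclusion.** The point stands as a defect in how the primary outcome is timed, and it should be fixed. It is certain that Section 5.0 anchors VAS to a procedure given in no arm, and that the documents contain no usable common time zero for the 1 to 72 h outcomes. It is conditional that ESP and infiltration would be compared at different times since surgery: this happens if each arm is timed from its own injection, and not if staff use a postoperative clock.

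The size of any bias cannot be computed from the documents. The assumed lags give gaps of 0.5 to 3.75 h, but the plan sets neither a floor nor a ceiling. Neither the sign nor the size of an effect on the 24 and 48 h VAS can be derived, so a reader should not infer that the primary result is biased towards ESP, or away from it. For opioid use, the direction depends on whether intraoperative doses count. LB versus SB within ESP is not affected.

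**What to change.** In Section 5.0, replace both anchors with one prespecified event that occurs in all three arms, either end of surgery or PACU arrival, chosen in advance. For example: *VAS at rest and on movement, opioid use, nausea and sedation are recorded 1, 24, 48 and 72 hours after end of surgery in all three groups; opioid totals count from that time.* In Section 8.0, apply the same time zero to the primary 24 and 48 h VAS and to satisfaction. Reporting intraoperative opioid separately is optional.

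Also record the ESP injection time, so that the LB versus SB duration question in Sections 1.0 and 8.0 can be analysed from injection as well. Infiltration time is not needed for that question. Keep injection times from the assessors, whom Section 4.0 describes as the only blinded staff, because these times could reveal the arm.

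The cost is two sentences in Section 5.0, a phrase in Section 8.0, and two recorded clock times: time zero in every patient and injection time in the ESP arms. No visits or assessments are added. The downside is that time since injection will still differ between ESP and infiltration at each assessment. No single clock equalises both, and the report should say so.

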3.0 Inclusion/Exclusion Criteria

Inclusion criteria:

- Pt undergoing VATS including but not limited to wedge or lobectomy at Indiana University Hospital,
- ASA 1,2,3 or 4
- Age 18 or older, male or female
- Desires regional anesthesia for postoperative pain control

Exclusion criteria:

- Any contraindication for Erector Spinae Plane block
- History of substance abuse in the past 6 months which would include heroin, marijuana or any other illegal street drugs
- Patient staying intubated after surgery
- Patient (home dose) taking more than 30mg PO morphine equivalent per day
- Known allergy or other contraindications to the study medications, which include dilaudid and bupivacaine.

- Pts. scheduled for a pleurodesis, decortication or esophagectomy at Indiana University Hospital
- BMI greater than 40.0.

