8.0 Statistical Considerations

Primary outcome: VAS score at 24 and 48 hours

Primary Research Hypothesis: ESP will provide lower pain scores compared to surgeon infiltration and ESP with LB will provide longer pain control than ESP with SB.

Secondary outcomes: Opioid usage after 1, 24, 48 and 72 hours. Pain scores using VAS at rest and on movement at 1, 24, 48 and 72 hours. Patient satisfaction scores at 24 and 48 hours. Nausea

scores at 1, 24, 48 and 72 hours. Sedation scores at 1, 24, 48 and 72 hours. Time to first bowel movement, incidence of urinary retention, and incidence of respiratory depression will be recorded as well.

Secondary Research Hypotheses: ESP blocks will show improved pain control, improved patient satisfaction scores, and decreased nausea and sedation scores compared to surgeon infiltration. Statistical analysis will be performed using a standard statistical program (SAS or SPSS). All data will be summarized (means, standard deviations, standard errors, and ranges for continuous variables; frequencies and percentages for categorical variables) by group. Demographic data will be compared between the three groups using ANOVA or chi-square tests as appropriate. The primary outcome, VAS at 24 and 48 hours, will be compared between the groups using repeated measures ANOVA; the model will include fixed effects for group, time, and the group by time interaction and random effects to allow correlations between the two times and different variances for the two times. Pain and satisfaction scores and opioid usage over time will be analyzed using repeated measures ANOVA. Nausea and sedation scores will be compared between groups at each time point using Mantel-Haenszel chi-square tests for ordered categorical data. Distributions of the continuous variables will be examined, and a transformation of the data (e.g. natural logarithm) or nonparametric tests will be used as necessary. A 5% significance level will be used for all comparisons.

Based on prior studies, the coefficient of variation for the VAS score at 24 and 48 hours is estimated to be 0.70. With a sample size of 40 per group, the study will have 91% power be able to detect a 60% decrease in VAS score between any two groups, assuming two-sided tests each conducted at a 5% significance level.

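### The 6-month call is meant to assess chronic postsurgical pain, but no preoperative pain score or home opioid dose is scheduled, so new pain or opioid use cannot be separated from what was already there

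*Combined protocol and SAP*

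**What the plan says.** Section 5.0 (Study Procedures) gives the late follow-up one purpose: "All patients will receive a phone call 6 months after surgery for assessment for chronic postsurgical pain". It continues: "They will be assessed on their pain score and narcotic usage by using the Brief Pain Inventory". Section 2.0 describes the same contact more loosely: "All patients will receive a phone survey 6 months after surgery to assess for pain and quality of life".

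The other pain scores in Section 5.0 are timed from the block: "All these parameters will be measured at 1, 24, 48 and 72 hours after the epidural or PVB". (An epidural and a PVB are not arms of this trial, but the timing is clearly after the block.) Section 8.0 repeats the times: "Pain scores using VAS at rest and on movement at 1, 24, 48 and 72 hours". Opioid use is recorded at the same four times.

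On who may enter, Section 3.0 excludes: "Patient (home dose) taking more than 30mg PO morphine equivalent per day". It also excludes substance abuse in the preceding 6 months. Pre-existing or chronic pain is not an exclusion.

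On baseline data, Section 8.0 says only: "Demographic data will be compared between the three groups using ANOVA or chi-square tests as appropriate". For the primary outcome, "the model will include fixed effects for group, time, and the group by time interaction and random effects" are specified, with no baseline covariate. Section 8.0 does not mention the 6-month call.

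**The concern.** Calling pain postsurgical is a statement about change or about cause. It needs either a value from before surgery or a rule for attributing pain to the operation. The plan has neither: no preoperative score is scheduled, and no text defines chronic postsurgical pain as new, worsened or located at the surgical site.

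The population makes this matter. A patient taking 20 mg oral morphine equivalent a day before surgery is eligible. If that patient still takes 20 mg at 6 months, the scheduled data look the same as those of a patient who started opioids because of the operation. The same applies to a patient with untreated long-standing pain.

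At stake is whether the 6-month result can carry the label the protocol gives it, and whether the comparison of 40 patients per group is as precise as it could be. A preoperative score that is not collected cannot be recovered later, except by recall.

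**Working it through.** **1. Is there a preoperative value anywhere?** The plan's contacts, in order:

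| Contact | Pain score scheduled? | Opioid dose recorded as data? |
|---|---|---|
| Clinic visit (4.0) | No; a copy of the consent form is handed over | No |
| POCU, day of surgery (4.0) | No; the study is explained and written consent taken | No; the home dose must be known for eligibility (3.0), but recording it is not stated |
| 1 to 72 h (5.0, 8.0) | Yes, VAS | Yes |
| 6 months (5.0) | Yes, Brief Pain Inventory | Yes |

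The 1-hour score cannot stand in for a baseline. Section 5.0 places the ESP block after sedation and before surgery, and the surgeon's infiltration during surgery. A score timed from either comes after sedation and local anaesthetic.

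**2. Is there a figure in the plan to reproduce?** No. The only power statement concerns VAS at 24 and 48 hours. The documents give no rate, variance, sample size or analysis for the 6-month outcome, so the calculations below rest on assumptions.

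**3. Precision of a continuous 6-month score.** Let r be the correlation between the baseline and 6-month scores (assumed 0.3 to 0.5). Adjusting for baseline multiplies the residual variance by 1 − r².

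- r = 0.3: 1 − 0.09 = 0.91, so 9% of the variance is removed.
- r = 0.5: 1 − 0.25 = 0.75, so 25% is removed.

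In sample-size terms, 40 adjusted patients per group are worth about 40/0.91 = 44 to 40/0.75 = 53 unadjusted patients.

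**4. Chance imbalance.** Assume 20% of patients have pre-existing pain. With 40 per group, the SD of the difference in that proportion between two groups is √(2 × 0.2 × 0.8 / 40) = √0.008 = 0.089, or 8.9 percentage points. The 95% range is about ±1.96 × 8.9 = ±17.5 points. As written, such an imbalance could be neither seen nor adjusted for.

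**5. Illustration for a binary outcome.** This needs more assumptions: pain is dichotomised; a share q of each group has pre-existing pain; all of it persists to 6 months; every such patient is classed as a case; and new pain arises independently. With true new pain p, the apparent rate is q + (1 − q)p. Take p as 30% and 15%. Power is for 40 per group, two-sided 5%.

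| q | Apparent rates | Difference (points) | Ratio | Power |
|---|---|---|---|---|
| 0% | 30% v 15% | 15 | 2.00 | 36% |
| 10% | 37% v 23.5% | 13.5 | 1.57 | 26% |
| 20% | 44% v 32% | 12 | 1.38 | 20% |
| 30% | 51% v 40.5% | 10.5 | 1.26 | 15% |

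For a mean score the result differs. If pre-existing pain adds the same amount on average in each group, the expected difference in means is unchanged and only the variance rises.

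**The case against.** The strongest case on the other side has four parts.

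*No counting rule exists.* A reader might infer that pre-existing pain will be counted as postsurgical, and that the reported frequency of chronic postsurgical pain will be overstated. The documents do not support either statement. They set no case definition and plan no such frequency. They also do not reproduce the inventory form, so whether it captures pain site or onset cannot be judged from them. What the documents support is that the two kinds of pain cannot be separated on the data scheduled. This part of the objection stands.

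*The comparison is randomised.* Pre-existing pain is balanced in expectation, and a valid test already allows for chance imbalance in its error rate. This stands too. Adjustment is a gain in efficiency, not the removal of a bias. Randomisation does not, however, help in attributing pain within a group to surgery.

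*The outcome is peripheral, and dilution is not established.* A reader might infer that the trial's treatment effects will be diluted. Section 8.0 lists the 6-month call as neither a primary nor a secondary outcome and names no analysis of it. The shrinkage in the last table follows only from the binary assumptions listed there. Even with no pre-existing pain, the assumed 30% v 15% has only 36% power, so a baseline would not rescue that comparison. This limits the weight of the point but does not remove it, because all patients are to be called for a stated purpose that the data cannot serve.

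*The home opioid dose is already ascertained.* Eligibility requires it to be known, so the gap for opioids is narrower than for pain. It is still a gap: nothing says that the dose is kept as trial data or set against use at 6 months.

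**Conclusion.** The point holds in a limited form. Because the plan schedules no preoperative pain score and no recording of the home opioid dose, while admitting patients with pre-existing pain and patients on up to 30 mg oral morphine equivalent a day, its 6-month data cannot show whether pain or opioid use is new, worse or merely continuing. This conclusion rests on the text alone.

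The size of the loss in precision rests on an assumed correlation: 9 to 25% of the variance of a continuous score for r between 0.3 and 0.5. The binary figures are illustrative and should not be read as an estimate of dilution in this trial.

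The primary outcome, the listed secondary outcomes and the unbiasedness of the group comparison are not affected. The point is a cheap improvement, worth making because the missing information cannot be recovered reliably after surgery.

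**What to change.** **Collect a baseline.** Amend Sections 4.0 and 5.0 so that, at the existing face-to-face contact in POCU, after written consent and before sedation and randomisation, each patient completes the same Brief Pain Inventory as at 6 months. Record as trial data the home opioid dose already checked for eligibility.

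**Use it.** State in Section 5.0 that 6-month pain and opioid use will be reported as new or increased relative to that baseline. Add to Section 8.0 a comparison of groups on the 6-month score adjusted for the baseline score, and summarise the baseline score and home opioid dose by group.

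**Cost.** A short amendment and a few minutes of questionnaire per patient, with the burden falling on the day of surgery. Treatment, sample size and the primary analysis do not change. The earlier clinic visit is not a ready alternative, because Section 4.0 has written consent taken in POCU; using the clinic would mean moving consent.

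For patients operated on before the amendment, the 6-month call could ask whether pain is at the surgical site and began after surgery. This relies on recall and is a weaker substitute.
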